7.2 Inclusion/Exclusion for Healthy Subjects

7.2.1 Healthy Subjects Inclusion Criteria

A healthy volunteer subject will be eligible for inclusion in this study if all of the following criteria are met:

- 1. Subject provides written informed consent as documented on the Institutional Review Board (IRB) approved informed consent document.
- 2. Subject is ≥ 18 years of age at Screening.
- 3. Male or non-pregnant, non-breast feeding female.
- 4. Females of childbearing (reproductive) potential must have a negative serum pregnancy test at Screening and a negative urine pregnancy test at Screening and Day 1, and agree to use an acceptable method of contraception throughout their participation in the study. Examples of acceptable methods of contraception include double barrier

methods (condom with spermicide jelly or diaphragm with spermicide), hormonal methods (oral contraceptives, patches or medroxyprogesterone acetate), or an intrauterine device with a documented failure rate of less than 1% per year. Abstinence may be considered an acceptable method of contraception at the discretion of the investigator.

NOTE: Females who have been surgically sterilized (e.g., hysterectomy or bilateral tubal ligation) or who are postmenopausal (total cessation of menses for >1 year) will not be considered "females of childbearing potential."

- 5. Subject has normal (or abnormal and clinically insignificant) laboratory values at screening.
- 6. Subject is medically normal with no significant abnormal findings at the Baseline physical examination.
- 7. Subject is capable of understanding the requirements of the study, is willing to comply with all the study procedures, and is willing to attend all study visits.
- 8. Subject has not consumed and agrees to abstain from taking any dietary supplements or non-prescription drugs (except as authorized by the Investigator and Medical Monitor) for 3 days prior to CRU admission through Follow-Up.
- 9. Subject has not consumed and agrees to abstain from taking any prescription drugs (except as authorized by the Investigator and Medical Monitor) during the 14 days prior to CRU admission through Follow-Up.

7.2.2 Healthy Subjects Exclusion Criteria

A healthy volunteer will **not** be eligible for inclusion in this study if any of the following criteria are met:

- 1. Subject has known allergy to rifaximin, rifampin, or other rifamycins, or to excipients and/or vehicles used in the formulation or other clinically significant allergies.
- 2. Subject has participated in an investigational drug or device study within the 30 days prior to Baseline (Day 1).
- 3. Subject is an employee of the site that is directly involved in the management, administration, or support of this study or is an immediate family member of the same.
- 4. Subject has any concurrent illness, disability or circumstance that may affect the interpretation of clinical data, could cause noncompliance with treatment or visits or otherwise contraindicates participation in this study in the opinion of the investigator.

Clinical Study Protocol Amendment 1 08Oct2018

- 5. Subject is pregnant or at risk of pregnancy, or is lactating.
- 6. Subject has a history of tuberculosis infection or has received treatment for a tuberculosis infection. To rule out tuberculosis infection, any one of the following criteria must apply: a) negative tuberculin skin test or negative tuberculosis blood test or b) if a subject has had a previous positive test, they must have a current negative chest X-ray (within 6 months of enrollment), or a current negative blood tuberculosis test.
- 7. Subject is positive for human immunodeficiency virus (HIV), hepatitis B and/or hepatitis C on Screening assessments.
- 8. Subject has an acute illness within 1 week of CRU admission.
- 9. Subject has donated plasma within 7 days of drug administration.
- 10. Subject has donated 1 or more pints of blood (or equivalent blood loss) within 30 days prior to drug administration.
- 11. Subject is positive for *Clostridium difficile* toxin via stool examination at Screening. NOTE: Results of stool tests must be confirmed as negative for Toxins A and B prior to Day -1. A stool sample must be collected during the Screening Period. Testing will be performed by enzyme immunoassay (EIA).
- 12. Subject has any of the following laboratory abnormalities:
 - a. Serum creatinine $\geq 1.5 \times$ the upper limit of normal;
 - b. Alkaline phosphatase, aspartate aminotransferase, alanine aminotransferase, or total bilirubin $\ge 2 \times$ the upper limit of normal;
 - c. Hemoglobin < 10.0 g/dL;
 - d. Absolute neutrophil count, or lymphocyte count ≤ 500 cells/ μ L.
- 13. Subject has known or suspected illicit drug use within the past year, or positive findings on urine drug screen, or has used any tobacco or nicotine products during the 6 months prior to screening and does not agree to refrain from using tobacco or nicotine products during the study.
- 14. Subject has received any type of vaccination within 7 days of drug administration.
- 15. Subject reports consumption of more than 2 alcoholic drinks daily, more than 14 alcoholic drinks within 14 days before the screening evaluation (an alcoholic drink is

Clinical Study Protocol Amendment 1 08Oct2018

defined as 1.5 oz liquor, one 12 oz can of beer, or 5 oz of wine), or consumption of any alcohol within 24 hours of first drug administration.

- 16. Subject has consumed grapefruit juice, grapefruits, or Seville oranges within 24 hours of first drug administration and does not agree to refrain from consuming these foods during the study.
- 17. Subject has consumed foods and substances that are known to inhibit and/or induce cytochrome P450 (CYP) or P-glycoprotein within 24 hours of first drug administration and does not agree to refrain from consuming these foods during the study, and/or has received treatment with any drugs known to be P-glycoprotein or CYP enzyme inducers or inhibitors within 30 days prior to first drug administration (see Appendix 2 or http://medicine.iupui.edu/flockhart/table.htm for a complete listing of excluded potential CYP inducers/inhibitors).
- 18. Subject has a history of Gilbert's disease or cholecystectomy.

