ascites, muscle spasms, pruritus, abdominal pain, anemia, depression, nasopharyngitis, abdominal pain upper, arthralgia, dyspnea, pyrexia, and rash.

In a study to characterize the pharmacokinetics of rifaximin in healthy subjects, administration of a single 550 mg oral dose to fasted and fed subjects resulted in mean AUC values of 11.1 ng.h/mL and 22.5 ng.h/mL, respectively. Multiple-dose twice daily (BID) or 3 times daily (TID) regimens in healthy subjects resulted in mean AUC values of 12.3 ng.h/mL (AUCtau, steady-state), and 9.3 ng.h/mL (AUCtau, steady-state), respectively (RFPK1007). Subjects with non-C IBS had mean AUCtau values following a single dose and multiple TID doses of 9.69 ng.h/mL and 16.0 ng.h/mL, respectively, reflecting an accumulation ratio (Rc; multiple-dose AUCtau/single-dose AUCtau) of 1.77 (RFPK1010). In subjects with hepatic impairment, systemic exposure is higher than that observed in healthy subjects. Following repeat dosing of a 550 mg BID regimen in hepatic impaired subjects in RFHE3002PK, mean steady-state AUCtau values of 118 ng.h/mL, 161 ng.h/mL, and 246 ng.h/mL were observed in Child-Pugh A, Child Pugh B, and Child-Pugh C subjects, respectively. In a study to determine the effect of P-glycoprotein inhibition on the pharmacokinetics of rifaximin, an in vitro substrate of P-glycoprotein, healthy subjects received a single oral dose of rifaximin 550 mg with or without a single oral 600 mg dose of cyclosporine, a potent P-glycoprotein inhibitor (RFDI1045). Systemic rifaximin exposure (as measured by plasma Cmax and AUC0- ∞) was increased following co-administration of rifaximin with cyclosporine in this study; mean Cmax was 40.0 ng/mL and mean AUC0-∞ was 314 ng.hr/mL following single doses of rifaximin plus cyclosporine compared with mean Cmax of 0.48 ng/mL and mean AUC0- ∞ of 2.53 ng.hr/mL following single-dose rifaximin alone. While the effect of the combination of hepatic impairment and P-glycoprotein on rifaximin pharmacokinetics has not been examined, a nonclinical toxicology study in dogs (BQG0004) provides greater than 30-fold and greater than 24-fold safety exposure margins over the mean exposures for the Pglycoprotein and hepatic impairment effects, respectively.

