6.1 Overview of Study Design

This is a Phase 4, open-label, repeat-dose, parallel-design study in 12 subjects with severe hepatic impairment (MELD 19 to 25 and MELD >25) and 6 healthy subjects with normal hepatic function. At least 6 hepatically impaired subjects will have MELD score >25. Efforts will be made to match subjects across groups in terms of age, weight, and sex. Eligible subjects will complete a Screening Period of up to 21 days prior to dosing (Day 1), a 7-day Treatment Period, and Follow-Up by phone 3 (+1) days later. Subjects will be admitted to the Clinical Research Unit (CRU) on the day prior to the initiation of dosing (Day -1; CRU admission). A plasma sample for PK analysis will be collected on Day 1 prior the first dose. Subjects will receive 550 mg rifaximin BID approximately 12 hour apart for 6 days beginning on Day 1 (Baseline). On Day 7 (End of Treatment; EOT), the final dose of study drug will be administered in the morning following an overnight fast of 10 hours and plasma samples for PK analysis will be collected pre-dose (within 1 hour of the dose) and at 0.25, 0.5, 0.75, 1, 1.5, 2, 4, 6, 8, 10, 12, 16, 20, and 24 hours post-dose. Additionally, a trough blood sample will be collected on Days 2-6, prior to administration of the first daily

Clinical Study Protocol Amendment 1 08Oct2018

dose of rifaximin. Subjects will reside in the CRU for 9 days and will be discharged following the final PK sample collection if safety parameters are acceptable to the Investigator. Each subject will be contacted for a follow-up phone call 3 + 1 days following end of treatment. The study schematic is presented in Figure 1.

Each dose will be administered with a total of 240 mL of water. During the first 4 hours after dose administration, subjects should not lie flat; they should be allowed to sit or stand. Subjects will receive standardized meals while in the CRU.

Subjects will discontinue non-study rifaximin on Day -1 and will only use rifaximin provided as study drug by the sponsor during the Treatment Period. Subjects may resume their prescription rifaximin use following CRU discharge.

Stool samples for microbiome analysis will be collected in the Screening Period and on Day 7 or 8.

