10.5.3 Child-Pugh Classification System

The Child-Pugh classification system for the severity of liver disease is listed below. The classification system determines severity of liver disease according to the degree of ascites (via clinical assessment), the serum concentrations of bilirubin and albumin, International Normalized Ratio, and the degree of encephalopathy.

		Score Assigned	
Parameter	1	2	3
Ascites	Absent	Mild	Moderate to Severe
Bilirubin, mg/dL	< 2	2-3	> 3
Albumin, g/dL	> 3.5	2.8-3.5	< 2.8
International Normalized Ratio	< 1.7	1.71 - 2.20	> 2.20
Encephalopathy*	None	Grade 1-2	Grade 3-4

Encephalopathy is classified as Grade 0-4 using the Conn scoring system below:

- Grade 0 = No personality or behavioral abnormality detected.
- Grade 1 = Trivial lack of awareness, euphoria or anxiety; shortened attention span, impairment of addition or subtraction.
- Grade 2 = Lethargy; disorientation for time; obvious personality change; inappropriate behavior.
- Grade 3 = Somnolence to semi-stupor, responsive to stimuli; confused; gross disorientation; bizarre behavior.
- Grade 4 = Coma; unable to test mental state.

Grade	Score
A: well-compensated disease	5 to 6
B: significant functional compromise	7 to 9
C: decompensated disease	10 to 15

A total score of 5 to 6 is considered grade A (well-compensated disease); 7 to 9 is grade B (significant functional compromise); and 10 to 15 is grade C (decompensated disease).

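### The six controls are meant to have normal hepatic function, but their criteria admit liver tests up to just under 2x ULN; one unrecognised hepatic abnormality would understate the rifaximin exposure ratio.

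*Combined protocol and SAP*

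**What the plan says.** Section 6.1 describes the reference group as "6 healthy subjects with normal hepatic function", and the primary objective in Section 5.1 uses the same idea.

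The healthy-subject criteria that bear on liver function are these:

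- **Section 7.2.2, exclusion 12b.** It lists "Alkaline phosphatase, aspartate aminotransferase, alanine aminotransferase, or total bilirubin" and excludes at 2x ULN or above.
- **Section 7.2.1, inclusion 5.** "Subject has normal (or abnormal and clinically insignificant) laboratory values at screening".
- **Section 7.2.1, inclusion 6.** "Subject is medically normal with no significant abnormal findings at the Baseline" physical examination.
- **Section 7.2.2, exclusion 4.** "Subject has any concurrent illness, disability or circumstance that may affect the interpretation of clinical data", among other grounds, in the investigator's opinion. The matching criterion for impaired subjects exempts cirrhosis; this one does not.
- **Section 7.2.2, exclusions 7, 15 and 18.** These cover positive hepatitis B or C (and HIV), alcohol intake above set limits, and Gilbert's disease or cholecystectomy.

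INR, albumin and GGT are all in the Screening panel (Section 10.4.4), but the healthy criteria set no numeric limit for them. MELD and Child-Pugh are assessed at Screening (Section 10.1.1) without restriction to impaired subjects, but neither is an eligibility criterion for controls.

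Section 12.6.1 compares log-transformed Cmax and AUCtau between groups by ANOVA with 90% confidence intervals; the synopsis adds CL/F. Section 12.7.1 plans no covariate adjustment. No sensitivity analysis on the controls' liver status is described.

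**The concern.** The label on the reference group and the rules that fill it do not match. A volunteer with an enzyme or bilirubin value between 1 and 2 times ULN passes 12b and can pass inclusion 5 on judgement. A raised INR or low albumin is subject to judgement alone.

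This matters more here than in many hepatic-impairment studies because rifaximin exposure depends strongly on liver status. Section 4.2.1 reports that "mean steady-state AUCtau values of 118 ng.h/mL, 161 ng.h/mL, and 246 ng.h/mL were observed in Child-Pugh A", B and C subjects respectively, against 12.3 ng.h/mL in healthy subjects dosed twice daily. The same six controls are the denominator for all twelve impaired subjects. One control with reduced hepatic function therefore raises the reference mean and makes the effect of severe impairment look smaller. The primary objective is to characterise the pharmacokinetics, so the size of that ratio is a main result of the study. With six controls, such a distortion would be hard to detect afterwards.

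**Working it through.** **Inputs from the protocol.** 12 impaired and 6 healthy subjects (Section 6.1); natural-log analysis with 90% intervals, so ratios are geometric mean ratios (Section 12.6.1); steady-state AUCtau of 12.3 in healthy subjects and 118, 161 and 246 ng.h/mL in Child-Pugh A, B and C (Section 4.2.1).

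**Assumptions.** The documents give neither the between-subject CV (taken as 30% to 100%) nor the exposure of a person with mildly raised liver tests and no cirrhosis (taken as r = 1.25 to 2 times healthy). Reported means stand in for geometric means.

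**Check on the inputs.** The plan gives no power or precision figure to reproduce. 161/118 = 1.36 agrees with the 36% difference between Child-Pugh B and A in Section 4.3. Relative to healthy, 118/12.3 = 9.59 and 246/12.3 = 20.0.

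**Step 1: bias from one control in six.** If one control has r times the healthy exposure, the control log mean rises by ln(r)/6. The control geometric mean is multiplied by r^(1/6), and the impaired/healthy ratio is divided by it.

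| r | r^(1/6) | Change in ratio |
|---|---|---|
| 1.25 | 1.038 | −3.7% |
| 1.5 | 1.070 | −6.5% |
| 2 | 1.122 | −10.9% |
| 3 | 1.201 | −16.7% |
| 5 | 1.308 | −23.5% |
| 9.59 (Child-Pugh A mean) | 1.458 | −31.4% |

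A 10% bias needs r = (1/0.9)^6 = 1.88.

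**Step 2: effect on the result.** With Child-Pugh C as a stand-in for the impaired group, the ratio of 20.0 becomes 20.0/1.122 = 17.8 at r = 2 and 20.0/1.458 = 13.7 at r = 9.59.

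**Step 3: comparison with sampling error.** The log-scale half-width of the 90% interval is t(0.95; 16 df) × s × √(1/12 + 1/6) = 1.746 × s × 0.5, with s = √ln(1 + CV²).

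| Assumed CV | s | Half-width (log) | Interval |
|---|---|---|---|
| 30% | 0.294 | 0.256 | ×/÷ 1.29 |
| 50% | 0.472 | 0.412 | ×/÷ 1.51 |
| 70% | 0.631 | 0.551 | ×/÷ 1.74 |
| 100% | 0.833 | 0.727 | ×/÷ 2.07 |

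The shift at r = 2 is ln(2)/6 = 0.116, below the half-width at every CV. The shift at r = 9.59 is ln(9.59)/6 = 0.377, which exceeds the half-width at CV 30% and comes close to it at CV 50%.

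**Step 4: precision.** The outlying control adds (5/16) × ln(r)²/6 to the expected pooled variance. At r = 9.59 and CV 50% the variance goes from 0.223 to 0.223 + 0.266 = 0.489. The half-width becomes 1.746 × 0.5 × √0.489 = 0.611, so the interval widens from ×/÷ 1.51 to ×/÷ 1.84.

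**The case against.** The strongest reply is that 12b is only a hard ceiling and other rules sit on top of it. A control must be medically normal, free of concurrent illness that could affect interpretation, negative for hepatitis B and C, within the alcohol limits and without Gilbert's disease. INR and albumin lack a numeric limit, but as Screening tests they still fall under inclusion 5, which bars clinically significant abnormalities. This stands. A reader might infer that the protocol lets people with known liver disease into the control group, and the criteria do not support that. They do leave room for disease nobody has recognised, or an abnormality accepted at discretion: inclusion 6 rests on a physical examination, exclusion 4 on opinion, and exclusion 15 on what the subject reports.

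A reader might also take 31% as the expected bias. That figure needs a control with cirrhosis-level exposure, and it divides a Child-Pugh A mean from one study by a healthy mean from another. Nothing in the documents ties values of 1 to 2 times ULN to such exposure.

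A third tempting step is to say that the Child-Pugh table in Section 10.5.3 marks such a control as impaired. With an assumed bilirubin ULN of 1.0 to 1.3 mg/dL, 12b allows values just below 2.0 to 2.6 mg/dL, and 2 to 3 mg/dL scores 2 points. But wholly normal values already total 5 and one extra point gives 6, both grade A. At a ULN of 1.0 the extra point does not arise.

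Finally, the argument does not cover every ratio. The documents give no data on how 25-desacetyl rifaximin changes with liver function. The wider interval is lost precision, not further bias toward 1.

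**Conclusion.** The concern holds as a mismatch between the stated reference population and the criteria that define it. The residual risk is an unrecognised or discretion-accepted hepatic abnormality in one of six controls. It would bias the rifaximin AUCtau ratio toward 1. CL/F is affected equally, being dose divided by AUCtau. Cmax probably moves the same way, since Section 4.3 reports it 6-fold higher in impaired subjects.

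Under the assumed 1.25- to 2-fold exposure, the bias is about 4% to 11%, smaller than the 90% interval half-width at every CV considered. The ceiling for one affected control, at the Child-Pugh A mean, is about 31%, with a wider interval as well. Even then the illustrative ratio is 13.7 rather than 20.0, so the conclusion that exposure is raised does not reverse; its size is understated. These sizes rest on assumed CVs, an assumed exposure for mild abnormality, and reported means used as geometric means.

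**What to change.** In Section 7.2.2, replace the 2x ULN limit in 12b with a requirement that total bilirubin, AST, ALT, ALP, INR and albumin lie within the laboratory's normal range at Screening, with one retest allowed. In Section 7.2.1, limit the allowance in inclusion 5 for insignificant abnormalities to tests other than liver tests. GGT could be added on the same terms, since it is already measured.

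If the sponsor keeps some tolerance so that controls can be matched on age and weight, pre-specify in the SAP a sensitivity analysis of the ratios that excludes any control with a liver test outside the normal range.

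The cost is a few more healthy screen failures for six places. All the tests are already in the Screening panel.

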7.3 Screen Failures

Screening evaluations will be used to determine eligibility of each subject for enrollment. Subjects who fail to meet eligibility criteria during the Screening period will be considered screen failures.

7.4 Premature Subject Discontinuation from Study Treatment or Study

Subjects will be encouraged to complete the study; however, they may voluntarily withdraw at any time. Subjects withdrawn from the study may be replaced.

In the event that a subject prematurely withdraws consent from further participation in the study for any reason other than an AE/SAE, the subject will be encouraged to complete the End of Treatment (Day 7) and all applicable assessments (except that plasma for PK will not be collected from subjects who early terminate the study) in order to obtain full data capture for that subject.

If a subject prematurely withdraws from the study at any time due to an AE or SAE, applicable End of Treatment (Day 7) assessments will be completed, and the subject will be followed for at least 14 days, or until resolution or stabilization of the condition resulting in withdrawal has been confirmed.

For all cases of premature withdrawal from the study, the investigator must provide the reason for discontinuation on the appropriate CRF page.

A decision by the investigator to discontinue a subject from study treatment and/or study participation should be discussed with the Sponsor.

8 Treatment Plan

8.1 Methods of Assigning Subjects to Treatment Groups

Not applicable

8.2 Randomization and Blinding

This is an open-label, single arm study. Study drug will not be blinded.

8.3 Concomitant Medications and Therapies

Subjects are not to take any medications (prescription or over the counter), alternative therapy(ies), or herbal supplement(s) during this study (14 days prior to dosing through endof study), unless the investigator, after discussion with the medical monitor (if feasible), determines use of medication is required; contraceptives are allowed during this study as defined in inclusion criterion. All medications, alternative therapy(ies), and/or herbal supplement(s) used during Screening and any ongoing or new medications / therapies taken while the subject is participating in the study will be recorded in the source documents (drug name, start and stop dates, and indication) and on the appropriate page of the electronic case report form (CRF).

For hepatically impaired subjects, stable doses of the following medications will be allowed during the study:

- Stable dose of antidepressants
- Stable opioid regimen. Stable regimen includes dose, pattern of use (e.g., as needed [PRN] or chronic dosing) combinations of opioids, and route of administration (e.g., oral or transdermal administration; parenteral administration is prohibited) for at least 4 weeks prior to Visit 2 (Baseline). The dose and regimen of opioid(s) should remain unchanged (i.e., < 20% change in dose and no change in opioid[s]) throughout the trial).
- Subjects who require concomitant antibiotic therapy with a once per week dosing regimen (e.g., ciprofloxacin 500-750 mg dose/week) for spontaneous bacterial

Clinical Study Protocol Amendment 1 08Oct2018 peritonitis (SBP) may participate in the study if they started their therapy at least 1 month prior to Visit 1 (Screening).

- Neurontin (gabapentin) and Lyrica (pregabalin) if a stable dose has been taken for at least 2 months prior to Visit 1 (Screening) and the dosage is expected to remain unchanged throughout the trial.
- Laxatives or stool softeners will be allowed to treat constipation at the discretion of the investigator but should be used sparingly to avoid diarrhea.

